7.2.3. Sensitivity Analyses of the Primary Endpoint

Missingness (not due to allergic reaction) will be evaluated for each vaccine type separately in each age group. If more than 5% of participants are missing their second active dose for either the Pfizer-BioNTech COVID-19 Vaccine or the Moderna COVID-19 Vaccine, a sensitivity analysis using the tipping-point approach will be conducted to assess the robustness of the primary analysis results. This analysis will only be conducted in the vaccine arm(s) with more than 5% missing. Participants missing both active doses will not be imputed. Tipping point analysis explores the influence of missingness on the overall conclusion from statistical inference by positing a wide spectrum of assumptions regarding the missingness mechanism (from less conservative to more conservative). The analysis finds a (tipping) point in this spectrum of assumptions, at which conclusions of the analysis change. After such a tipping point is determined, clinical judgment can be applied as to the plausibility of the assumptions underlying this tipping point.

7.2.4. Additional Analysis of the Primary Endpoint

The rate of reaction for active dose 1 will be summarized in the following manner:

$$\frac{\# \text{ participants experiencing a reaction per section 7.2.1 to active dose 1}}{\# \text{ participants who received active dose 1}}$$

The rate of reaction for active dose 2 will be summarized in the following manner:

$$\frac{\# \text{ participants experiencing a reaction per section 7.2.1 to active dose 2}}{\# \text{ participants who received active dose 2}}$$

No imputation will be performed for any reason for any participant who does not receive the second active dose. The rate of reaction for each dose will be summarized separately for the Pfizer- BioNTech and Moderna COVID-19 vaccines.

7.3. Secondary Endpoints

All secondary endpoints will be analyzed for participants enrolled under version 1.0 through 4.0. If sufficient numbers of children are enrolled, then adults 18 years of age and older will be also be analyzed separately from children.

7.3.1. Secondary Endpoint 1

Endpoint: The proportion of participants who experience a severe (Grade 3 or higher per [CoFAR Grading Scale for Systemic Allergic Reactions Version 3.0](#)) systemic allergic reactions within the 90-minute post-vaccination observation period to either dose of each vaccine.

Computation: A Grade 3 or higher systemic allergic reaction, categorized as yes or no, is defined as a participant having a Grade 3 or higher (per CoFAR Grading Scale V3.0) systemic allergic reaction to either active dose 1 or active dose 2 (categorized as yes) or to neither active dose (categorized as no).

Participants who do not have a systemic allergic reaction to the 1st active dose but missing data for their 2nd active dose will be removed from this analysis (complete case analysis).

Analysis: This analysis will be carried out as outlined in Section 7.2.2. A sensitivity analysis will be carried out as outlined in Section 7.2.3.

7.3.2. Secondary Endpoint 2

Endpoint: The proportion of participants who experience an anaphylactic reaction (Levels 1-3) per Brighton Collaboration Criteria within the 90-minute post-vaccination observation period to either dose of each vaccine.

Computation: An anaphylactic reaction (Levels 1-3) per Brighton Collaboration Criteria, categorized as yes or no, is defined as a participant having an anaphylactic reaction (Levels 1-3) per Brighton Collaboration Criteria to either active dose 1 or active dose 2 (categorized as yes) or to neither active dose (categorized as no).

Participants who do not have a systemic allergic reaction to the 1st active dose but missing data for their 2nd active dose will be removed from this analysis (complete case analysis).

Analysis: This analysis will be carried out as outlined in Section 7.2.2. A sensitivity analysis will be carried out as outlined in Section 7.2.3.

7.3.3. Secondary Endpoints 3/4

Objective (paired)
Assess the proportion of participants with systemic allergic reactions to the Pfizer-BioNTech COVID-19 Vaccine in the HA/MCD population by dose
Endpoint
The proportion of participants who experience a systemic allergic reaction (CoFAR Grade 2 and above regardless of tryptase, or CoFAR Grade 1 with elevated tryptase [1.2 x baseline plus 2 ng/ml]) within the 90-minute post-vaccination observation period to the first dose and to the second dose conditional on no systemic allergic reaction to the first dose.
Statistical Test
Endpoint will be analyzed using an exact McNemar's test.
Checks & Diagnostics
This analysis will not be carried out if there are no systemic allergic reactions.
Model Results Presentation
Proportions and 95% exact confidence intervals will be presented for the 1 st and 2 nd dose. The mid p-value will be reported using an exact McNemar's test.
Placebo & Pfizer -BioNTech COVID-19 Vaccine (1 st)

Placebo & Pfizer -BioNTech COVID-19 Vaccine (2nd)

Placebo + Pfizer	placebo	1 st	2 nd
Pfizer	1 st	2 nd	

SAS Code

```
*** Paired doses;
proc freq data = d_w order=data;
  title "Paired";
  where group = 'HA/MCD';
  tables D1*D2 / riskdiff;
  exact mcnem riskdiff / midp;
run;
```

R Code

```
library(exact2x2)
t <- with(d_w %>% filter(group == 'HA/MCD'), table(D1, D2))
mcnemar.exact(t, conf.level=.95)
mcnemarExactDP(n=sum(t),
  m=t[1,2]+t[2,1],
  x=t[2,1])
```

Supportive Statistical Analyses

A sensitivity analysis will be performed using a GEE logistic regression model & NLMeans macro to obtain the proportion difference and 95% confidence interval. There will be no adjustment for covariates.

```
*** Paired doses (Sensitivity);
proc genmod data = d_l;
  title "Paired (Sensitivity)";
  where dose in ('D1','D2') & group = 'HA/MCD';
  class id dose;
  model resp(event = '1') = dose / dist=binomial link = logit;
  repeated subject=id / type = ind;
  lsmeans dose / e ilink diff exp;
  store out=genmod;
  ods output coef = coeffs;
run;
%NLMeans(instore=genmod, coef=coeffs, link=logit, title= Paired Prop
Diff);
```

Handling of Missing Data

Participants with missing data for their 2nd active dose for reasons other than systemic allergic reactions in their 1st active dose will be removed from this analysis (complete case analysis).

Participants with missing data for their 2nd active dose because of a systemic allergic reaction to their 1st active dose (inherent missingness given the current design) will be examined using an extreme case scenario (replacement of all 2nd active dose missing by either yes or no). If the results from this extreme case scenario differs and if there is at least 10 systemic allergic reactions in the 1st active dose a tipping point analysis will be conducted.

Notes

The same analysis will be repeated for the Moderna COVID-19 Vaccine.

Objective (priming)

Assess the difference in proportions of participants with systemic allergic reactions after the second Pfizer-BioNTech COVID-19 Vaccine dose (not placebo arm) versus the first vaccine dose within the placebo arm in the HA/MCD population.

Endpoint

The proportion of participants who experience a systemic allergic reaction (CoFAR Grade 2 and above regardless of tryptase, or CoFAR Grade 1 with elevated tryptase [1.2 x baseline plus 2 ng/ml]) within the 90-minute post-vaccination observation period to the second dose conditional on no systemic allergic reaction to the first dose in the Pfizer-BioNTech COVID-19 Vaccine arm and the first active dose in the Placebo- Pfizer-BioNTech COVID-19 Vaccine arm.

Model Specification

- Endpoint is as defined above.
- Endpoint will be analyzed using Barnard's unconditional exact test.

Model Checking & Diagnostics

This analysis will not be carried out if there are no systemic allergic reactions in the 1st dose among the placebo arm and/or 2nd dose among the Pfizer arm.

Model Results Presentation

Proportions, 95% exact unconditional confidence intervals and p-value will be presented for the 1st dose among Placebo & Pfizer and 2nd dose among the Pfizer arm.

Placebo & Pfizer-BioNTech COVID-19 Vaccine (1st)

Pfizer-BioNTech COVID-19 Vaccine (2nd)

Placebo + Pfizer	placebo	1 st	2 nd
Pfizer	1 st	2 nd	

SAS Code

```
*** Priming;
proc freq data = d_1;
  title "Priming";
  where group = 'HA/MCD' &
    ((dose = 'D1' & Placebo = 'Yes') | (dose = 'D2' & Placebo = 'No'));
  tables dose*resp / riskdiff;
```

```
exact riskdiff barnard;
run;
```

Supportive Statistical Analyses

If there is an issue with the calculation of the Barnard's Exact Unconditional Test, we will perform a univariate logistic regression.

```
*** Priming (Sensitivity);
proc genmod data = d_1;
  title "Priming (Sensitivity)";
  where group = 'HA/MCD' &
    ((dose = 'D1' & Placebo = 'Yes') | (dose = 'D2' & Placebo = 'No'));
  class dose;
  model resp(event = '1') = dose / dist=binomial link = logit;
  lsmeans dose / e ilink diff exp;
  store out=genmod;
  ods output coef = coeffs;
run;
%NLMeans(instore=genmod, coef=coeffs, link=logit, title= Priming Prop
Diff);
```

Handling of Missing Data

Participants with missing data for their 2nd active dose for reasons other than systemic allergic reactions in their 1st active dose will be removed from this analysis (complete case analysis).

Participants with missing data for their 2nd active dose because of a systemic allergic reaction to their 1st active dose (inherent missingness given the current design) will be examined using an extreme case scenario (replacement of all 2nd active dose missing by either yes or no). If the result from this extreme case scenario differs and if there is at least 10 systemic allergic reactions in the 1st active dose a tipping point analysis will be conducted.

Notes

The same analysis will be repeated for the Moderna COVID-19 Vaccine.

7.3.4. Secondary Endpoint 5

Objective (First dose comparison to Placebo)

Assess the proportion of participants with systemic allergic reactions to the Pfizer-BioNTech COVID-19 Vaccine in the HA/MCD after adjusting for placebo

Endpoint

The proportion of participants who experience a systemic allergic reaction (CoFAR Grade 2 and above regardless of tryptase, or CoFAR Grade 1 with elevated tryptase [1.2 x baseline plus 2 ng/ml]) within the 90-minute post-vaccination observation period to the first dose of the Pfizer-BioNTech COVID-19 Vaccine after adjusting for placebo administration

Model Specification

- Endpoint is as defined above.
- Endpoint will be analyzed using Barnard's unconditional exact test.

Model Checking & Diagnostics

This analysis will not be carried out if there are no systemic allergic reactions for the placebo dose.

Model Results Presentation

Proportion difference, 95% exact unconditional confidence interval and p-value will be presented for the comparison between 1st dose (active arm) and placebo dose (placebo arm)

Placebo + Pfizer-BioNTech/Placebo + Moderna COVID-19 Vaccine (**placebo**) vs Pfizer-BioNTech COVID-19 Vaccine (**1st**)

Placebo + Pfizer/Placebo + Moderna	placebo	1st	2 nd
Pfizer	1 st	2 nd	

SAS Code

```
*** 1st dose comparison to Placebo;
proc freq data = d_1;
  title "1st dose comparison to Placebo";
  where group = 'HA/MCD' &
    ((dose = 'P1' & Placebo = 'Yes') |
    (dose = 'D1' & Placebo = 'No' ));
  tables dose*resp / riskdiff;
  exact riskdiff barnard;
run;
```

Supportive Statistical Analyses

If there is an issue with the calculation of the Barnard's Exact Unconditional Test, we will perform a univariate logistic regression. NLMeans macro will be used to obtain the proportion difference and 95% confidence interval. There will be no adjustment for covariates

```
*** 1st dose comparison to Placebo (Sensitivity);
proc genmod data = d_1;
  title "1st dose comparison to Placebo (Sensitivity)";
  where group = 'HA/MCD' &
    ((dose = 'P1' & Placebo = 'Yes') |
    (dose = 'D1' & Placebo = 'No' ));
  class id dose;
  model resp(event = '1') = dose / dist=binomial link = logit;
  lsmeans dose / e ilink diff exp;
  store out=genmod;
  ods output coef = coeffs;
run;
%NLMeans(instore=genmod, coef=coeffs, link=logit, title= 1st dose
comparison to Placebo Prop Diff);
```

Handling of Missing Data

Participants with missing data for their placebo or 1st active dose will be removed from this analysis (complete case analysis).

Notes

The same analysis will be repeated for the Moderna COVID-19 Vaccine.

7.3.5. Secondary Endpoint 6

Endpoint: The proportion of participants who experience a systemic allergic reaction (CoFAR Grade 2 and above) within 48 hours of either dose of each vaccine.

Computation: A Grade 2 or higher systemic allergic reaction, categorized as yes or no, is defined as a participant having a Grade 2 or higher (per CoFAR Grading Scale V3.0) systemic allergic reaction within 48 hours to either active dose 1 or active dose 2 (categorized as yes) or to either active dose within 48 hours (categorized as no). Due to the nature of patient reported events, any systemic allergic reaction reported within 2 days after the date of injection will be counted as occurring within 48 hours.

Participants who do not have a systemic allergic reaction to the 1st active dose but missing data for their 2nd active dose will be removed from this analysis (complete case analysis).

Analysis: This analysis will be carried out as outlined in Section 7.2.2. A sensitivity analysis will be carried out as outlined in Section 7.2.3.

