### 3.2. Primary Endpoints

The two primary endpoints are:

1. The proportion of participants who experience a systemic allergic reaction (CoFAR Grade 2 and above regardless of tryptase, or CoFAR Grade 1 with elevated tryptase [ $1.2 \times$  baseline plus 2 ng/ml]) within the 90-minute post-vaccination observation period to either dose of the Pfizer-BioNTech COVID-19 Vaccine
2. The proportion of participants who experience a systemic allergic reaction (CoFAR Grade 2 and above regardless of tryptase, or CoFAR Grade 1 with elevated tryptase [ $1.2 \times$  baseline plus 2 ng/ml]) within the 90-minute post-vaccination observation period to either dose of the Moderna COVID-19 Vaccine

A participant can have a reaction to either dose 1 or dose 2 (but not to both doses since a participant who has a reaction meeting qualifying criteria to dose 1 will not be able to receive the second dose) or to neither dose.

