### **6.5. Premature Discontinuation of Investigational Agent**

Vaccination will be prematurely discontinued for any participant for any of the following reasons:

- Participant has a CoFAR Grade 2 or higher systemic allergic reaction regardless of tryptase, or a CoFAR Grade 1 reaction with elevated tryptase [1.2 x baseline plus 2 ng/ml] that is at least possibly related to the first dose of the vaccine. If the systemic allergic reaction took place after the participant has left the vaccination clinic and no tryptase measurements are available, Grade 1 events will not constitute criteria for discontinuation, but counseling by a study physician will be required (see below).
- The investigator believes that it is no longer in the best interest of the participant to receive the second vaccination

In the above cases, the participant will be asked to return for his/her next in clinic study visit during which reactogenicity symptoms will be reviewed (electronic diary review or return and review of paper diary), adverse events (AEs) and concomitant medications will be recorded, and pre-vaccination biospecimens will be obtained per protocol.

Vaccination may be prematurely discontinued for any participant for any of the following reasons:

- If a participant has a Grade 1 (per [CoFAR Grading Scale](#)) systemic allergic reaction with no evidence of systemic mast cell activation to the first dose of either the Pfizer-BioNTech COVID-19 Vaccine or Moderna COVID-19 Vaccine, he/she will receive counseling by a study physician and will be allowed to receive a second dose if he/she so chooses.
- Because the placebo will consist of a normal saline injection, a reaction to placebo will not require termination from subsequent active vaccination, if the participant is willing to proceed following counseling.
- If a participant becomes pregnant between the first and second doses of vaccine, she will receive counseling by a study physician and will be allowed to receive a second dose if she so chooses.

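### The paired dose 1 v dose 2 McNemar test has almost no observed data in one of its two deciding cells, and the SAP does not say which fill gives the reported p-value

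*SAP*

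**What the plan says.** - **Test.** SAP 7.3.3 (paired objective) uses an exact McNemar test in the HA/MCD population, separately for each vaccine: "The mid p-value will be reported using an exact McNemar's test".
- **Who gets dose 2.** Protocol 3.2 states that "a participant who has a reaction meeting qualifying criteria to dose 1 will not be able to receive the second dose". Protocol 3.1 and 6.5 give the same rule, and 6.5 limits it to a reaction "that is at least possibly related to the first dose of the vaccine".
- **Dose 2 missing for other reasons.** SAP 7.3.3: participants whose dose-2 data are missing "for reasons other than systemic allergic reactions in their 1st active dose will be removed from this analysis".
- **Dose 2 missing because of a dose-1 reaction.** The SAP calls this "inherent missingness given the current design" and says that these participants "will be examined using an extreme case scenario (replacement of all 2nd active dose missing by either yes or no"). If the results differ, and "if there is at least 10 systemic allergic reactions in the 1st active dose a tipping point analysis will be conducted".
- **Code.** The SAS and R excerpts cross-tabulate D1 by D2 and show no fill step. How the dataset d_w is derived is not printed.
- **Elsewhere.** Protocol 14.4.3 plans by-dose estimates with exact confidence intervals and names no test of dose 1 against dose 2. SAP 7.2.4 gives the same two rates without imputation. Protocol 14.6 says that every primary and secondary objective rests on a two-sided superiority test. SAP 11 lists only the as-treated definition as a change from the protocol.

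**The concern.** McNemar's test uses only discordant pairs: reacted at dose 1 but not dose 2, against the reverse. Because qualifying dose-1 reactors do not receive dose 2, whatever enters the first of these cells is supplied almost entirely by the analyst. The SAP names two opposite ways to supply it and reports one p-value without tying it to either.

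The choice can decide the answer. If the missing outcomes are set to yes, every dose-1 reactor becomes concordant. The p-value then depends on the dose-2 count alone and can only point to dose 2 as the worse dose. Whether risk differs by dose is a stated secondary interest, so a spurious signal against dose 2 would mislead.

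**Working it through.** **Inputs.** HA/MCD planned maximum of 1020 per vaccine and about 10 reactions over both doses (Protocol 14.7). Two-sided testing (Protocol 14.6). A level of 0.05 is stated for the primary test only and is assumed here. The split of risk between doses is not in the documents and is assumed. The sizes 680 and 510 are illustrative: enrolment is capped, not fixed, and SAP 7.3 says "All secondary endpoints will be analyzed for participants enrolled under version 1.0 through 4.0".

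**The plan's own figure.** 1020 × 0.01 = 10.2 expected reactions. The Clopper-Pearson interval for 10/1020 is (0.0047, 0.0180), which agrees with the stated (0.005, 0.018). The documents give no figure for the McNemar test itself.

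**Formula.** Let b = no at dose 1, yes at dose 2, and c = yes at dose 1, no at dose 2. With X ~ Bin(b + c, 0.5) and k = min(b, c), mid-p = 2P(X ≤ k) − P(X = k), and 1 if b = c. Under the no fill, c is the number of dose-1 reactors. Under the yes fill, c = 0 and mid-p = 0.5^b: b = 4 gives 0.0625 and b = 5 gives 0.031.

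| Reactions, dose 1 v dose 2 | No fill | Yes fill |
|---|---|---|
| 10 v 0 | 0.001 | no discordant pairs |
| 9 v 1 | 0.012 | 0.500 |
| 7 v 3 | 0.227 | 0.125 |
| 5 v 5 | 1.000 | 0.031 |
| 3 v 7 | 0.227 | 0.008 |
| 20 v 5 | 0.002 (dose 1 worse) | 0.031 (dose 2 worse) |

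**How often mid-p < 0.05.** Exact enumeration with x1 ~ Bin(n, p1) and x2 given x1 ~ Bin(n − x1, p2):

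| Risk at dose 1, dose 2 | n | Yes fill | No fill |
|---|---|---|---|
| 0.5%, 0.5% | 1020 | 57% | 4.1% |
| 0.5%, 0.5% | 680 | 25% | 3.4% |
| 0.5%, 0.5% | 510 | 11% | 2.5% |
| 0.3%, 0.3% | 1020 | 19% | 3.1% |
| 0.3%, 0.3% | 680 | 5.6% | 1.7% |
| 0.3%, 0.3% | 510 | 2.0% | 0.9% |
| 0.1%, 0.1% | 1020 | 0.4% | 0.3% |
| 0.8%, 0.2% | 1020 | 5.5%, always towards dose 2 | 47.5% |

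**Unfilled data.** The result depends on the software and on how the rows are prepared. The R step table(D1, D2), run in base R on 1010 no/no, 5 no/yes and 5 yes/missing, returns a D1 = yes row of 0, 0 without a warning. The values m = 5 and x = 0 are then passed on, as under the yes fill. If the incomplete rows are removed first, the table has one row and t[2,1] stops with an error. The exact2x2 functions and the SAS step were not run, and they may give an error or no result.

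**What appears beside the p-value at 5 v 5.** Dose 1 is 5/1020 = 0.49% (0.16 to 1.14). Dose 2 shown conditionally is 5/1015 = 0.49% (0.16 to 1.15). Under a consistent yes fill, dose 2 is 10/1020 = 0.98%.

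**Tipping-point trigger.** At 0.5% per dose, the probability of at least 10 dose-1 reactions is 3.5%, 0.3% and 0.03% for n = 1020, 680 and 510.

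**The alternative p-value.** An exact binomial on observed reactions, with probability n1/(n1 + n2), is almost the same as the no-fill exact McNemar: 0.581 for both at 8 v 5, and 0.002 for both at 10 v 0. Now suppose that 1% of people react to whichever dose comes first, so that x2 = 0 and there is no dose effect. The binomial needs six dose-1 reactions (2 × 0.5^6 = 0.031), and P(Bin(n, 0.01) ≥ 6) = 94%, 67% and 40% at n = 1020, 680 and 510. The no-fill mid-p needs only five (0.5^5 = 0.031), which gives 97%, 81% and 58%.

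**The case against.** The strongest reply is that the SAP has already seen the problem. It names the missingness, requires both extreme fills and adds a conditional tipping-point step, so a reader shown both p-values would see any disagreement. It removes people only when dose 2 is missing for reasons other than a dose-1 reaction, which keeps dose-1 reactors in. Protocol 3.2 treats reactions to both doses as impossible, which also points to the no fill. That version holds its size when everyone carries the same risk. All this stands. What remains is that nothing ties the reported mid-p to a fill, and the tipping-point step would seldom run if risk is split evenly.

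Three stronger readings are tempting, and the documents do not support them.

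- *The planned test has a 57% false-positive rate.* That figure belongs to the yes fill at the planned maximum size and 0.5% per dose. The text leans the other way. Since the derivation of d_w is not printed, the code excerpt does not show that no fill is applied. Unfilled runs cannot simply share the figure, because some end in an error.
- *A significant p-value will sit beside two near-identical proportions.* This happens only if dose 2 is displayed conditionally. A consistent yes fill shows 0.49% v 0.98%.
- *The deciding cell is empty by design.* It is nearly so. A dose-1 reaction judged unrelated could still be followed by dose 2.

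It is also fair to say that neither fill is right under every mechanism. If susceptible people would react to any dose, the yes fill is the correct one, and the no fill or the binomial is misled by their removal at dose 1.

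**Conclusion.** The point holds in limited form. SAP 7.3.3 reports a paired p-value whose value, and sometimes direction, depends on outcomes for doses never given, and it does not say which assumption is primary. With about the planned number of reactions split evenly, the two named versions give 0.031 and 1.00.

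The error rates rest on an assumed split by dose, equal risk across people, a 0.05 level and the sizes shown. They fall quickly with lower risk or fewer participants. Only one secondary p-value per vaccine is affected, and no decision rule is attached to it. The dose-specific proportions with their exact intervals, the SAP 7.2.4 rates and a GEE on unfilled data stand. It is worth correcting before database lock, and it does not threaten the primary analysis.

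**What to change.** **Preferred.** Drop the McNemar p-value from the paired objective. Report dose-1 risk (reactors over dose-1 recipients) and conditional dose-2 risk (reactors over dose-2 recipients) with exact confidence intervals, as Protocol 14.4.3 and SAP 7.2.4 already provide. Keep the GEE risk difference on unfilled long data as support only when both doses have events, because the logit estimate does not exist when one dose has none. Record the change in SAP 11 and note there the exception to Protocol 14.6.

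**If a p-value is kept:**
- State in advance that the primary version counts observed reactions per dose: the no fill or the near-equivalent exact binomial.
- Show the yes fill beside it as a sensitivity bound, whatever the dose-1 count.
- Print the fill step in the code.
- Label the result a comparison of dose-specific risks, not a within-person dose effect, because removal of susceptible people at dose 1 can produce significance with no dose effect.

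**Cost.** SAP wording before database lock. The two rates and the GEE are already specified, and no clinical rule or data collection changes.

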7.2.2. Primary Analysis of the Primary Endpoint

If systemic allergic reactions are observed, we will compare the proportions of participants experiencing a systemic allergic reaction to the Pfizer-BioNTech COVID-19 Vaccine and independently to the Moderna COVID-19 Vaccine between the HA/MCD and comparison populations. The point estimate of the difference in proportions between populations within each vaccine is estimated as p_1-p_0 with $p_1=x_1/n_1$ and $p_0=x_0/n_0$ and will be reported, together with the corresponding 95% exact unconditional confidence interval. The proportion difference will be tested using a Barnard's Exact Unconditional Test with a two-sided test using the central method of doubling the one-sided p-value. No multiplicity adjustment will be applied to these two primary endpoints.

```
*** Primary Analysis (Barnard's);
ods output BarnardsTest=BarnardsTestOutput;
proc freq data = d_1 order = data;
  title "Primary";
  where dose = 'E' and protocol<5;
  tables group*resp / riskdiff;
  exact riskdiff barnard;
* High computational power, only run on an as needed basis;
run;
```

The p-value is equal to (BARNARDSTESTOUTPUT.NVALUE1)*2 where BARNARDSTESTOUTPUT.NAME1='XPL_RDIF1'.

```

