# R: Primary Analysis (Barnard's) p-value
library(exact2x2)
t <- with(d_1 %>% filter(dose == 'E' and protocol<5),
table(group,resp))
uncondExact2x2(t[1,2],sum(t[1,]),
t[2,2],sum(t[2,]),
alternative = "less",
parmtype = "difference",
method   = "score",
midp     = TRUE,
control  = ucControl(nPgrid=5000),
conf.int = FALSE)
```

Exact unconditional confidence limits for the risk difference are obtained with SAS procedure PROC FREQ and the RISKDIFF option in the EXACT statement. These RISKDIFF options request exact unconditional 95% confidence limits for the risk (proportion) and risk difference for the 2x2 table respectively. PROC FREQ computes the confidence limits by the tail method, which inverts two separate one-sided exact tests of the risk difference, where the tests are based on the score statistic (Chan and Zhang 1999). The size of each one-sided exact test is at most $\alpha/2$, and the confidence coefficient is at least $(1-\alpha/2)$.

If there is an issue with the calculation of the Barnard's Exact Unconditional Test, we will perform the Risk difference estimates, asymptotic 95% confidence intervals, and p-values using SAS procedure PROC FREQ and the RISKDIFF option without an EXACT statement.

```
*** Primary Analysis (Asymptotic);
proc freq data = d_1 order = data;
  title "Primary";
  where dose = 'E' and protocol<5;
  tables group*resp / riskdiff;
run;
```

Additionally, we will compare the proportion of participants experiencing a systemic allergic reaction (as defined in section 7.2.1) between HA/MCD adult (18 years and older at enrollment) and HA/MCD child (less than 18 years of age at enrollment) populations for each vaccine separately. Children who qualified for the study on the basis of uncontrolled allergic asthma will be excluded from this analysis. The point estimate of the difference in proportions between adult and child populations within each vaccine will be estimated along with its corresponding 95% exact unconditional confidence interval. The proportion difference will be tested using a Barnard's Exact Unconditional Test with a two-sided test using the central method of doubling the one-sided p-value. No multiplicity adjustment will be applied.

In the event that there are not enough subjects in a particular population, the reaction rate will be described descriptively.

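### In SAP 7.3.3 (paired), RISKDIFF on the dose-1-by-dose-2 table conditions on dose-1 response, so it does not give the promised exact interval for the dose-1 proportion, and its risk difference is not dose 1 v dose 2.

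*SAP*

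**What the plan says.** SAP 7.3.3 (Secondary Endpoints 3/4, paired objective) compares the first and second active doses within HA/MCD participants. The test is stated as "Endpoint will be analyzed using an exact McNemar's test". For results, the section promises "Proportions and 95% exact confidence intervals will be presented for the 1 st and 2 nd dose", together with the McNemar mid p-value. The SAS block uses the wide data set and contains "tables D1*D2 / riskdiff" and "exact mcnem riskdiff / midp".

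The SAP shows elsewhere what it takes RISKDIFF to do. In 7.2.2 the option is used on "tables group*resp / riskdiff", with population as the row and reaction as the column. The estimate there is the difference between the two rows' response proportions. The accompanying text says: "These RISKDIFF options request exact unconditional 95% confidence limits for the risk (proportion) and risk difference for the 2x2 table respectively".

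Three other provisions matter:
- Protocol 3.2 and 6.5: a participant with a qualifying reaction to dose 1 does not receive dose 2.
- SAP 7.3.3, missing data: for those participants, the missing dose-2 result is examined by setting all of them to yes, or all to no.
- Protocol 14.4.3: exact intervals are planned for the first-dose proportion and for the second-dose proportion conditional on no reaction to the first.

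**The concern.** RISKDIFF takes each row of a 2x2 table as a group and the column as the outcome. With population in the rows, as in 7.2.2, that is the intended comparison. With dose-1 response in the rows, the groups become dose-1 reactors and dose-1 non-reactors, and the outcome is reaction to dose 2. The dose-1 proportion is then a row total divided by the sample size. It is neither a row risk nor the overall column risk, so no interval for it appears in the output.

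The design sharpens the problem. The reactor row has no observed dose-2 outcomes, so whatever RISKDIFF prints for that row comes from the fill rule and not from data. At stake is the interval for one of the two by-dose proportions, and the chance that a risk difference printed under the title Paired is tabled as the difference between doses.

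**Working it through.** **Inputs.** n = 1020 HA/MCD participants per vaccine and 10 reactors are the scenario in Protocol 14.7. The split of the 10 between doses is not in the documents. I assume 6 to dose 1 and 4 to dose 2, and show a range below.

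**Check of the interval method.** The documents give no figure for the paired difference, so there is none to reproduce. Clopper-Pearson gives (0, 0.0036) for 0/1020 and (0.0047, 0.0180) for 10/1020. Protocol 14.7 prints (0, 0.0036) and (0.005, 0.018), which agree.

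**Formulas.** Label the cells (dose 1/dose 2) a = yes/yes, b = yes/no, c = no/yes, d = no/no.
- Dose-1 proportion: (a+b)/n
- Dose-2 proportion over all n: (a+c)/n
- Paired difference: (a+b)/n - (a+c)/n = (b-c)/n
- RISKDIFF: a/(a+b) - c/(c+d)

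**Numbers for the 6/4 split** (c = 4, d = 1010)

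| Dose 2 of the 6 dose-1 reactors | a, b | RISKDIFF | Paired difference |
|---|---|---|---|
| all set to no | 0, 6 | 0/6 - 4/1014 = -0.0039 | (6-4)/1020 = +0.0020 |
| all set to yes | 6, 0 | 6/6 - 4/1014 = +0.996 | (0-4)/1020 = -0.0039 |
| left missing | row empty | undefined | not available from this table |

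The sign is opposite under both fills.

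**Intervals for the same split.** The reactor row gives 0/6 (0 to 0.459) or 6/6 (0.541 to 1). The proportion wanted for dose 1 is 6/1020 = 0.0059 (0.0022 to 0.0128). The non-reactor row gives 4/1014 = 0.0039, which is the conditional dose-2 proportion of endpoint 4.

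**Range over splits** (dose 1/dose 2: 10/0, 7/3, 5/5, 3/7)
- All no: RISKDIFF is 0, -0.0030, -0.0049, -0.0069. The paired difference is +0.0098, +0.0039, 0, -0.0039.
- All yes: RISKDIFF is 1.000, 0.997, 0.995, 0.993. The paired difference is 0, -0.0029, -0.0049, -0.0069.

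**Is it only the fill, or the sort order?** No. Take a table with both rows populated: a = 2, b = 8, c = 5, d = 1005. RISKDIFF is 2/10 - 5/1010 = 0.195, and the paired difference is (8-5)/1020 = 0.0029. Reversing both rows and columns gives 1005/1010 - 8/10 = 0.195 again, so the sort order does not turn it into the paired difference.

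**The case against.** A reader might infer that the SAP's dose-1 v dose-2 comparison as a whole is wrong, or that endpoints 3 and 4 have no valid analysis. The documents do not support that, and the case against the stronger reading is good.

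- The main paired analysis promises two proportions with intervals and a mid-p. It does not ask this line for a difference. The SAP assigns the difference to the GEE/NLMeans sensitivity step, which uses one record per dose. Without any fill, the difference in observed proportions in the 6/4 example is 6/1020 - 4/1014 = +0.0019, with the right sign.
- The exact McNemar test and the R code work from the discordant pairs, and RISKDIFF does not alter them.
- SAP 7.2.4 defines each dose's reaction rate with the correct numerator and denominator and no imputation, and Protocol 14.4.3 states the estimands correctly.
- The non-reactor row is not wasted, because it is exactly endpoint 4.
- The value near 1 arises only under the all-yes fill, which the SAP itself treats as an extreme case. With no fill there is simply no output, and a difference near 1 for an event of about 1% would be noticed.

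All of this stands, and it limits the point. It does not remove it. SAP 7.2.4 mentions no intervals, and nothing in the paired SAS block supplies the exact interval for dose 1. The all-no fill is the harder case to notice: -0.0039 looks plausible and has the wrong sign.

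**Conclusion.** The point holds in a limited form. As written, the RISKDIFF requests in the paired block omit the promised exact interval for the dose-1 proportion. They also print a risk difference that is undefined without imputation and otherwise fixed almost entirely by it: between -0.007 and 0 with all no, and between 0.993 and 1.000 with all yes, over the splits examined. The paired difference stays between -0.0069 and +0.0098 over the same splits.

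The conclusion about what the code estimates needs no assumption beyond the SAP's own use of RISKDIFF in 7.2.2. The sizes rest on the protocol's scenario of 10 reactors in 1020 and on assumed splits by dose. This is a coding error on secondary endpoints that should be corrected before the code is run. It does not touch the primary analysis.

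**What to change.** In SAP 7.3.3 (paired):
1. Keep the D1-by-D2 table and the exact McNemar mid-p, and remove RISKDIFF from both the TABLES and the EXACT statements.
2. Take the dose-1 proportion and its Clopper-Pearson interval from a one-way exact binomial table of D1, with the event level set to a reaction.
3. Take the endpoint-4 proportion and interval from a one-way exact binomial table of D2, restricted to participants with no dose-1 reaction and an observed second dose. The restriction matters. In the 6/4 example, a one-way D2 table run after the fill would give 4/1020 (all no) or 10/1020 (all yes) in place of 4/1014.
4. Report any dose-1 v dose-2 difference only from the GEE/NLMeans step already listed, or from a matched-pairs interval.
5. Apply the same change to the Moderna repeat.

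The cost is a few lines of SAS code, with no change to data or design.
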